7.6 DISCONTINUATION OF STUDY TREATMENT

The following events are considered sufficient reasons for considering the discontinuation of a subject from the study:

- An adverse event (AE) that in the judgement of the investigator may cause severe or permanent harm
- Subject withdraws consent
- Subject lost to follow-up
- Death
- Protocol violation

8. TREATMENT & BLUE LIGHT PARAMETERS

8.1 PRE-EXPOSURE SKIN CARE

Subjects will wash their face with CeraVe® Facial Cleanser prior to study treatment. Subsequently, the mixed contents of Kerastick® (see section 8.2) will be applied topically with gloves to the designated target treatment area. After an incubation period of ninety minutes, subjects will wash their face again with CeraVe® Facial Cleanser.

8.2 INVESTIGATIONAL MEDICATION

Kerastick[®] is the dosage form of Levulan[®], which consists of a low-density polyethylene tube with two glass ampules and a sponge applicator tip covered with a protective cardboard sleeve and cap. Each Levulan[®] Kerastick[®] applicator contains one ampule containing 354 mg of aminolevulinic acid HCL (ALA) and one ampule of 1.5 mL of vehicle. Upon mixing both ampules, the concentration of ALA becomes 20%.

8.2.1 SUPPLIER

Levulan® Kerastick® will be supplied by DUSA pharmaceuticals, Inc.

8.2.2 RECEIPT & STORAGE OF STUDY DRUG

The Principle Investigator or designee is responsible for taking inventory of each shipment of study drug received. All investigational drug will be stored in a locked, safe area to prevent unauthorized access at the Heater Road clinic at Dartmouth Hitchcock Medical Center. The study drug will be stored as directed on the package insert.

8.2.3 ACCOUNTABILITY

The Principle Investigator or designee is responsible for keeping a record of all investigational drug that is dispensed during the study.

8.2.4 HANDLING & DISPOSAL OF DRUG

Any unused product will be documented, discarded, and need not be returned to DUSA pharmaceuticals, Inc. If any study drug is lost or damaged, its disposition will be documented in the subject's source documents.

8.3 LIGHT TREATMENT

8.3.1 BLUE LIGHT TREATMENT

Blue light will be administered to the lips using the BLU-U® blue light (417 nm) PDT illuminator. The prescribed treatment time will be 16 minutes and 40 seconds, which will result in a total light dose of approximately 10 J/cm² delivered at 10 mW/cm². Light exposure will be controlled with a timer. The investigator, subject, and anyone else in the light treatment room will wear appropriate protective eyewear at all times.

8.3.2 SUPPLIER

The BLU-U light and Omnilux revive^{2TM} device is available at the dermatology clinic at Dartmouth Hitchcock Medical Center.

8.4 POST-EXPOSURE SKIN CARE

Subjects will be given verbal and written post-treatment instructions to clean treatment sites with warm water and CeraVe® Facial Cleanser®, and to apply topical petrolatum ointment until any weeping or crusting has subsided. Subjects will also apply chapstick with sun protection. All subjects will be instructed to avoid direct sun exposure and to apply a sun block with at least a sun protection factor (SPF) of 30 (Neutrogena® SPF 100) for at least 48 hours after each treatment.

9. CLINICAL ASSESSMENTS

Efficacy and safety assessments during the treatment phase of the study will be done at the intervals specified in Section 4. The same investigator should complete the evaluations for a given subject throughout the study; however, if the assigned investigator is not available, another investigator with overlapping experience with the subject can complete the evaluation.

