- Subjects who are immunocompromised

Study Procedures

The study will consist of a screening visit, up to three scheduled treatments, and two scheduled office visits. There can be a three-day window period for each scheduled visit in order to accommodate the subject's schedule and unforeseen scheduling conflicts.

 Visit 1 (Screening): Subjects can be screened for the study up to two weeks before Visit 2 (Baseline). During screening, the study will be reviewed, written informed consent obtained, and eligibility confirmed. If applicable, the washout from prohibited medications or treatments will be determined at this visit.

- 2. Visit 2 (Baseline): Following signed, written informed consent and confirmation of eligibility, all subjects will have their lips photographed. Medical history, dermatologic exam, urine pregnancy test (if applicable), review of concomitant medications, clinical evaluations, and tolerability assessments will be performed at this visit. Study medication application to clean skin will be followed by a ninety minute incubation period under occlusion. Subsequently, patients will be exposed to blue light therapy for 16 minutes and 40 seconds. Post-therapy assessments will be performed afterwards, as well as education on appropriate sun protection methods.
- 3. Visits 3-4: Subjects will return every six weeks for up to two additional treatments. Treatment will be discontinued once the patient has achieved clinical clearance. Tolerability assessments, study medication application, blue light therapy, post-therapy assessments, and photographs will be performed.
- 4. Visit 5-6 (End of Study): Subjects will return 12 and 24 weeks after the last treatment for clinical evaluations, tolerability assessments, and photographs.

Study Measurements

Primary efficacy will be assessed by the investigator for the following:

- Clearance will be estimated clinically as minimal (0%-25%), mild (26%-50%), moderate (51%-75%), good (76%-99%), or complete (100%).
- Results will also be evaluated by comparing photographs before and immediately after treatments, and 12 and 24 weeks after the last treatment.

Secondary endpoints will include the following:

 Subject reported pain during and after blue light illumination using a Visual Analogue Scale (VAS) from 0 (no pain) to 10 (worst pain imaginable).

	Percent of patients with adverse events.				
	Safety will be assessed by the investigator as follows:				
	 Local Skin Reactions: Assessment of swelling, 				

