7. RESEARCH DESIGN & METHODS

This is a single center, investigator initiated, nonrandomized, open-label, proof of concept study of PDT with blue light and topical Levulan® in the treatment of actinic cheilitis.

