9.2 PHYSICIAN PERFORMED ASSESSMENTS

9.2.1 EFFICACY ASSESSMENTS

Primary efficacy will be assessed by the investigator for clearance from baseline (Visit 2) to the end of study (Visit 6; week 36). Clearance will be estimated clinically as minimal (0%-25%), mild (26%-50%), moderate (51%-75%), good (76%-99%), or complete (100%). Clinical photographs will also be taken at Visit 2 to 6. Care will be taken to avoid including any identifying landmarks, such as characteristic tattoos, birthmarks, etc.

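### Both the live clearance rating and the planned photograph comparison are made by an investigator who knows the visit and treatment history; the baseline and follow-up photographs should be read with their time order hidden

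*Combined protocol and SAP*

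**What the plan says.** Section 7 describes a "single center, investigator initiated, nonrandomized, open-label, proof of concept study of PDT". There is no comparator.

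Section 9.2.1 defines the primary measure: "Primary efficacy will be assessed by the investigator for clearance from baseline (Visit 2) to the end of study (Visit 6; week 36"). The estimate is a clinical judgement in five bands, from minimal (0%-25%) to good (76%-99%) and complete (100%).

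On who rates, Section 9 says: "The same investigator should complete the evaluations for a given subject throughout the study". If that person is unavailable, "another investigator with overlapping experience with the subject can complete the evaluation".

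On photographs, Section 9.2.1 says: "Clinical photographs will also be taken at Visit 2 to 6". The synopsis (Section 3, Study Measurements) already uses them under investigator-assessed primary efficacy: "Results will also be evaluated by comparing photographs before and immediately after treatments, and 12 and 24 weeks after the last treatment". The Section 4 schedule lists this comparison among the physician efficacy assessments at Visits 2 to 6.

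The protocol does not mention masking to visit, a random reading order, a reader who has not met the subject, or a check of agreement between the photographs and the live rating. Section 12.1 on analysis says only that a biostatistics section will help.

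**The concern.** With no control arm, the efficacy statement rests on the change that the rater perceives from baseline. That rater knows which visit it is and how many treatments have been given. Section 7.3 also ends treatment at clinical clearance and names no separate judge, so a rater at follow-up may be revisiting a judgement already made by the same team.

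The photographs could serve as a check on that rating. As planned they do not, because the investigator also makes the comparison and can see which image came first. The two measures share the same source of bias, so agreement between them would say little about whether the rating is sound.

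Time order can be hidden without a control arm. Section 5 notes that controlled trials are lacking, and Section 12.1 plans publication, so the credibility of this rating matters even in a proof-of-concept study.

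**Working it through.** No stated figure is in dispute. The sample size of 20 (Section 7.2) comes without power or precision inputs and cannot be re-derived. The check is mainly a reading of the text, with three short calculations.

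**1. Is either primary measure masked?**

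| Measure | Where | Who | Time order hidden? |
|---|---|---|---|
| Live clearance band | 9.2.1, 9 | Investigator following the subject, or a back-up who already knows the subject | No |
| Photograph comparison | 3, 4 | Investigator | Not stated |
| Subject's global assessment | 9.3.1 | Subject | No |

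None of the three is protected from expectation.

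**2. Are usable images available?** Clearance is measured from Visit 2, and photographs are taken at Visits 2 to 6. Visits 5 and 6 fall 12 and 24 weeks after the last treatment (Section 7.3), while Section 7.5 expects local reactions to settle in one to two weeks. Follow-up images should therefore rarely reveal their timing through an acute reaction. Images taken immediately after treatment may do so, which is why the masked pairs should use the pre-treatment image from Visit 2. Section 9.2.1 also asks that photographs avoid identifying landmarks, which helps masking.

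**3. Reading load.** 20 subjects × 2 follow-up visits = 40 pairs at most, and fewer with drop-out.

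**4. Possible size (assumed inputs; the documents give none).**
- Each subject is 1/20 = 5 points. If expectation moves 2 to 4 subjects from good to complete, the rate moves by 2/20 = 10 to 4/20 = 20 points.
- Example at the upper end: 8/20 = 40% (exact 95% CI 19% to 64%) becomes 12/20 = 60% (36% to 81%).
- Alternative model: observed rate = p + (1 − p)m, where p is the true complete-clearance rate and m is the chance that a subject not cleared is rated as cleared. The shift is (1 − p)m. For p from 0.3 to 0.7 and m from 0.1 to 0.3, it runs from 0.3 × 0.1 = 3 points to 0.7 × 0.3 = 21 points.

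Both calculations use a complete-clearance rate for illustration. The protocol sets no responder cut-off.

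**The case against.** The strongest reply is that this is declared a "nonrandomized, open-label, proof of concept study" with no hypothesis test and no success threshold. An unmasked rating is open and expected in such a study, and the intervals at 20 subjects are so wide that imprecision limits any claim at least as much as bias does. That stands as a limit on severity. It does not remove the gap, because a larger sample or a narrower interval would not correct a shared expectation.

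A reader might also infer several things that the documents do not support:

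- *That the photographs go unused.* A comparison is already planned; what is missing is masking of time order.
- *That the investigator is the only source of an efficacy rating.* Subjects rate their own improvement under Section 9.3.1, although that rating is unmasked too.
- *That the same-investigator rule is the fault.* It keeps ratings within a subject consistent and should stay for live ratings.
- *That a masked reading is free, or is the only bias control available.* No staffing figures are given, and someone must code and shuffle the files. A live assessor who does not treat the subject would be another option.
- *That the efficacy result will be falsely positive.* Nothing in the documents shows the size of any bias.

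Two practical objections also stand. The scale starts at 0% and has no band for worsening, so a masked reader who prefers the baseline image needs a defined outcome. And nothing shows that photographs can separate good from complete clearance, so disagreement with the live rating need not mean bias. For that reason, agreement should not be made a condition for the efficacy statement.

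**Conclusion.** The point holds as an inexpensive design improvement; it does not identify an error or contradiction. Both components of primary efficacy are judged by an investigator who knows the visit and treatment history, and nothing hides which image is baseline. Expectation bias in the primary result is therefore uncontrolled.

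Its size is unknown. The 10 to 20 points rest wholly on the assumption that 2 to 4 of 20 subjects are reclassified, and the 3 to 21 points rest on assumed values of p and m. Neither range is an estimate for this trial.

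Masked reading would hide time order only. It would not supply a control group or separate a treatment effect from natural change in the lesions.

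**What to change.** In Section 9.2.1, specify how the planned comparison of the Visit 2 pre-treatment image with the Visit 5 and Visit 6 images is to be read:

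- The existing investigators read the pairs at study end. Where one is available, the reader is an investigator who did not follow that subject; Sections 7.5, 9 and 10 all refer to more than one investigator.
- The coordinator codes the files, shuffles the pairs and randomises left/right order. Visit and treatment count are hidden.
- The reader first records which side is better, or no difference, and then the degree of difference on the protocol's percentage bands.
- After decoding, a pair in which the baseline image was preferred is recorded as 'no improvement or worse'.
- The result is reported as a supportive analysis beside the live clinical rating, with agreement described and no agreement threshold.

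Keep the same-investigator rule for live ratings.

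The cost is a coding step by the coordinator and, on a rough estimate, a few hours of investigator time for up to 40 pairs. No new visit or procedure is needed. The downside is that masking is partial: a reader may recognise some lips, especially if no investigator unfamiliar with the subject is available, and photographs may not distinguish good from complete clearance. The report should state both limits.

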9.1 DEMOGRAPHIC INFORMATION

After signing the informed consent paperwork, each subject will be given a short questionnaire regarding their personal demographic information (i.e. gender, age, race, ethnicity, highest educational degree, annual income, marital status). Each subject will be assigned a Subject ID number (1-20), which will be documented on each of their study materials.

9.2 PHYSICIAN PERFORMED ASSESSMENTS

9.2.1 EFFICACY ASSESSMENTS

Primary efficacy will be assessed by the investigator for clearance from baseline (Visit 2) to the end of study (Visit 6; week 36). Clearance will be estimated clinically as minimal (0%-25%), mild (26%-50%), moderate (51%-75%), good (76%-99%), or complete (100%). Clinical photographs will also be taken at Visit 2 to 6. Care will be taken to avoid including any identifying landmarks, such as characteristic tattoos, birthmarks, etc.

9.2.2 PRE & POST-TREATMENT SAFETY ASSESSMENTS

A study physician will complete post-treatment assessments based upon visual observation of *swelling, vesiculation/pustulation, erosion/ulceration, erythema, flaking/scaling,* and *crusting.* The assessment will be based upon the scaling system below:

Swelling	Grade 0: not present
	Grade 1: slight, lesion specific edema
	Grade 2: palpable edema extending beyond individual lesions

	Grade 3: confluent or visible edema
	Grade 4: marked swelling, very easily noticeable from a
	distance
Vesiculation/Pustulation	Grade 0: not present
	Grade 1: only vesicles
	Grade 2: <50% pustules with or without vesicles
	Grade 3: > 50%, but <75% pustules with or without vesicles
	Grade 4: >75% pustules with or without vesicles
Erosion/Ulceration	Grade 0: not present
	Grade 1: lesion specific erosion
	Grade 2: erosion extending beyond individual lesions
	Grade 3: erosion >50%
	Grade 4: black eschar or ulceration
Erythema	Grade 0: not present
	Grade 1: slightly pink <50%
	Grade 2: pink or light red >50%
	Grade 3: red 50-75%
	Grade 4: severe redness, >75%, very easily noticeable from a
	distance
Flaking/Scaling	Grade 0: not present
	Grade 1: isolated scale, specific to lesions
	Grade 2: scale <50%
	Grade 3: scale >50%, but <75%
	Grade 4: scale >75%, very easily noticeable from a distance
Crusting	Grade 0: not present
	Grade 1: isolated crusting
	Grade 2: crusting <50%
	Grade 3: crusting >50%
	Grade 4: crusting >75%, very easily noticeable from a distance

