	vesiculation/pustulation, erosion/ulceration, erythema,				
	flaking/scaling, and crusting using a five-point ordinal scale				
	(0: none to 4: severe) will be conducted after each				
	treatment visit. The presence or absence of				
	hyperpigmentation in the treatment area will also be				
	documented after each treatment visit.				
	Subjects will be asked to rate their pain using a VAS both				
	during and after blue light treatment.				
	PDT Reactions: Other than those specified under local skin				
	reactions.				
	Adverse Events: Evaluation of any reported local or				
	systemic events outside the treatment area and other than				
	those specified under local skin reactions.				
Study Endpoints	Primary Endpoints:				
	Clearance will be estimated as a percentage improvement				
	from baseline.				
	Secondary Endpoints:				
	Tolerability of treatment and tabulation of reported local				
	and systemic adverse events.				
Study Duration	24 to 36 weeks				
Total Sample Size	20				

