7.2 SCREENING & ELIGIBILITY

Male and female subjects \geq 18 years of age with a diagnosis of actinic cheilitis will be asked to participate in this study after the objectives, methods, and potential hazards of the study have been fully explained, and they have signed the informed consent form. The Principle Investigator will be responsible for keeping a record of all subjects who sign an informed consent form for entry into this study. A total of 20 subjects will be enrolled in this study.

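### Swelling is graded by visual observation, but Grade 2 is defined by palpation and Grade 3 takes in any visible edema, so slight visible edema at a lesion fits both Grade 1 and Grade 3

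*Combined protocol and SAP*

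**What the plan says.** Section 9.2.2 states the method for all six signs, swelling first: "A study physician will complete post-treatment assessments based upon visual observation of" those signs. The swelling row starts at Grade 0 for no swelling. Its lowest positive grade is worded "Grade 1: slight, lesion specific edema". The step above that is defined by touch and by spread: "Grade 2: palpable edema extending beyond individual lesions". The one after it offers two alternatives, either of which is enough: "Grade 3: confluent or visible edema". The top grade is for marked swelling that is conspicuous from afar.

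The synopsis describes the instrument as "flaking/scaling, and crusting using a five-point ordinal scale", running from 0 (none) to 4 (severe). The Schedule of Assessments (Section 4) places it at Visits 2 to 6. No section adds palpation to the method, sets a minimum for visible edema, or says which grade to record when two apply.

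**The concern.** The method and the definitions do not match. A grade that rests on touch sits inside an assessment made by eye. The grade above it can be met simply because the edema is seen, which is true of everything found by looking. A slight reaction could then be recorded as Grade 1 by one physician and Grade 3 by another, each following the text.

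The row is likely to be used. Section 7.5 names edema among the expected transient reactions, and tolerability is a secondary endpoint. The synopsis also defines adverse events as events other than the listed local skin reactions, so this grade is the main physician record of how severe swelling was. The patient's telephone rating (Section 9.3.4) is a weak cross-check: its Grades 2 to 4 are anchored to thirds of the face, whereas the treatment is to the lips. Section 9 prefers the same investigator throughout for a given subject but allows a substitute, so two readings of the row could occur within one subject and look like a change over time.

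**Working it through.** The plan gives no figure to reproduce here. The check is whether each state of edema falls in exactly one grade, and whether each grade can be reached, under the stated visual method. The inputs are the method sentence and the row definitions in Section 9.2.2.

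| State of edema | Grades met on the wording | Found by looking? |
|---|---|---|
| (a) Slight, at the lesion, seen | 1, and 3 through the visible limb | Yes |
| (b) Past the lesions, felt and seen, not confluent | 2, and 3 through the visible limb | Yes |
| (c) Past the lesions, felt but not seen | 2 only | No |
| (d) Slight, at the lesion, not seen | 1 only | No |

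1. **Overlap.** State (a) meets two grades that are not adjacent. Grade 3 − Grade 1 = 2 points; 2/4 = 0.5, half of the 0–4 range. State (b) meets two adjacent grades.
2. **Reachability.** The only state that belongs to Grade 2 alone is (c), and looking cannot detect it. Under the stated method, every edema that is found also qualifies for Grade 3.
3. **Palpation added.** If physicians also palpated, (c) would give Grade 2 a use. State (a) would still meet Grades 1 and 3.
4. **A tie-break alone.** Recording the highest grade met, with the row otherwise unchanged, would send (a) to Grade 3. The definitions have to change as well.
5. **Effect of one subject.** Section 7.2 says "A total of 20 subjects will be enrolled in this study". At the first session with all 20 treated and graded, one misgraded subject moves a proportion by 1/20 = 0.05, or 5 percentage points. At later sessions the shift is 1/n. The documents do not give n, and it may be below 20 because treatment stops at clinical clearance (Sections 7.3 and 7.4).

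Two neighbouring rows also have overlapping cut-points. In erythema, Grade 2 (>50%) contains the extent range of Grade 3 (50–75%), leaving only the shade of red to separate them. In crusting, Grade 3 (>50%) contains Grade 4 (>75%).

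**The case against.** The best defence is that a physician will read the row as the ordered scale the synopsis says it is: slight and at the lesion, then felt more widely, then confluent or plainly visible, then marked. On that reading slight lesion edema is Grade 1 and nobody would call it Grade 3. The study is also single-arm, open-label and proof of concept, so no comparison between arms can be biased. No discontinuation reason in Section 7.6 refers to a swelling grade. Section 9 asks for one investigator per subject.

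Much of this stands as a limit on importance, and it shows that a 2-point difference is the widest divergence the wording allows, not an expected error. It does not remove the conflict. The sensible reading needs palpation, which the method sentence does not provide for, and a threshold for visible, which the row does not contain. One investigator per subject limits drift within a subject but not differences between raters.

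Three stronger readings are tempting, and the documents do not support them:

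- **Grade 2 can never be assigned.** This is true only on a strictly visual reading; a physician who also palpates could use it.
- **The fault is peculiar to swelling.** Only the clash between palpable and visible is peculiar to that row. Overlapping grades also occur in the erythema and crusting rows.
- **A Grade 3-or-higher rate shifts by 5 points at each session.** The documents name no such rate. They plan the percentage of patients with adverse events and a tabulation of local and systemic adverse events, and they do not secure 20 subjects at every session.

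**Conclusion.** The inconsistency is real and lies within Section 9.2.2. Slight, visible, lesion-specific edema satisfies both Grade 1 and Grade 3, and Grade 2 has no distinct place without palpation that the plan does not mention. This conclusion rests on the wording of the method sentence and the swelling row, and on no other section qualifying either.

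Its reach is limited. It affects the descriptive swelling part of the secondary tolerability data. A reader might infer that the efficacy result is at risk; it is not, because clearance is assessed on a separate scale (Section 9.2.1). The range of disagreement is up to 2 of 4 scale points for the same lip. The frequency of disagreement cannot be derived from the documents. The figure of 5 percentage points per misgraded subject assumes the first session and full enrolment. The correction is worth making before enrolment because the reaction is expected and the edit is small.

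**What to change.** Reconcile the method with the definitions: delete palpable and visible from the swelling row and grade on visible extent.

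- Grade 0: unchanged.
- Grade 1: confined to individual lesions.
- Grade 2: past individual lesions but not confluent.
- Grade 3: confluent but not meeting Grade 4.
- Grade 4: the present definition, whatever the extent.

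Add that the highest grade met is recorded.

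Dropping slight from Grade 1 gives a place to more-than-slight swelling that stays at one lesion. Letting Grade 4 override extent removes an overlap between Grades 3 and 4. States (a) and (b) above then fall in Grades 1 and 2 respectively, unless they are marked enough for Grade 4. States (c) and (d), which are not seen, are recorded as Grade 0, as the visual method implies.

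In the same edit, make the extent ranges exclusive for erythema Grades 2 and 3 and for crusting Grades 3 and 4.

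The cost is one revised swelling row on the case report form, plus the cut-points in the other two rows, with no added visit or staff. The small downside is less direct comparability with any data graded on the current wording.

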10. ASSESSMENT OF ADVERSE EVENTS

Safety precautions, such as the use of highly experienced investigators, frequent office visits, and close monitoring of clinical and laboratory findings (pregnancy tests) have been implemented in the protocol and are specified in the Schedule of Assessments (see Section 4). All unexpected physical examination findings will be captured as Adverse Events (AEs) when deemed medically significant by the investigator. Potential events that are anticipated post-treatment include erythema and pain. Other, less frequent potential events associated with any dermatological PDT include bleeding, crusting, numbness, itching, blistering and dryness, all of which tend to be transient.

A qualified physician associated with the study will be available to assess clinical signs and symptoms that may be indicative of an AE. Any clinical sign or symptom that was not present at baseline and are not included in the expected side effect profile of PDT will be recorded as an AE. AEs may be reported spontaneously by the patient or elicited

through open (non-leading) questioning during each visit and up until the end of the period of observation (week 36; Visit 6).

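### The vesiculation/pustulation row never grades how far vesicles extend, so vesicle-only reactions of any extent score Grade 1, the lowest non-zero grade

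*Combined protocol and SAP*

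**What the plan says.** The protocol has the study physician grade six local skin reactions. The synopsis (Section 3) describes a five-point ordinal scale, "0: none to 4: severe", and Section 9.2.2 defines the grades sign by sign. For vesiculation/pustulation, Grade 0 is absence of the sign. The lowest positive grade reads "Grade 1: only vesicles", with no extent attached. A percentage first appears one step up, in "Grade 2: <50% pustules with or without vesicles", and it belongs to the pustules. The third step moves that pustule percentage to between 50% and 75%, and the top of the row is "Grade 4: >75% pustules with or without vesicles".

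By contrast, the flaking/scaling row of the same table is graded by the extent of the sign itself, up to "Grade 4: scale >75%, very easily noticeable from a distance".

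Section 10 names erythema and pain as the reactions to anticipate. It then lists less frequent possible reactions to PDT: "bleeding, crusting, numbness, itching, blistering and dryness, all of which tend to be transient". Pustules are not in that list. The same section says that new signs which "are not included in the expected side effect profile of PDT will be recorded as an AE". The synopsis likewise defines both its PDT-reaction category and its adverse event category as excluding the specified local skin reactions, of which vesiculation is one.

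**The concern.** The row combines two signs, but the percentage belongs to only one of them. No grade mentions the extent, size or confluence of vesicles. On a scale whose top is labelled severe, a reader of a tabulated grade would expect a higher number to mean a worse reaction of the named kind. For blistering without pustules that does not hold, because every positive reaction receives the same number.

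Tolerability is the stated secondary endpoint, safety is part of the study objective, and there is no control arm. What the study can say about blistering rests mainly on this row. If extent is not written down at the visit, it may not be recoverable afterwards.

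**Working it through.** There is no stated figure to reproduce, and no alpha, power or variance enters. The check is an enumeration of the Section 9.2.2 definitions over vesicle extent (V) and pustule extent (P).

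| Pustules (P) | Vesicles (V) | Grade |
|---|---|---|
| 0% | 0% | 0 |
| 0% | any, from about 1% to 100% | 1 |
| above 0%, below 50% | any, including 0% | 2 |
| above 50%, below 75% | any, including 0% | 3 |
| above 75% | any, including 0% | 4 |

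Three things follow.

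1. When P = 0, the grade depends only on whether V is above zero. The attainable grades are 0 and 1, so 4 − 1 = 3 of the 4 positive grades are out of reach.
2. When P is above 0, the grade does not depend on V. Vesicle extent is therefore never graded anywhere in the row.
3. A lip wholly covered by vesicles scores 1. A lip with a few pustules and no vesicles scores 2.

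One alternative reading is to treat 0% pustules as a case of "Grade 2: <50% pustules with or without vesicles". The explicit vesicles-only category rules that out, and the grade would still not depend on V.

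Next, is vesicle extent graded somewhere else?

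- **Adverse event severity (Section 10.2.3).** The mild/moderate/severe grade applies to adverse events. The synopsis exclusion and the Section 10 rule together steer expected local reactions away from it. The route is not fully closed: Sections 10 and 10.1 leave room for findings the investigator judges medically or clinically significant, and Section 10.2.2 covers important medical events.
- **Two-day telephone call (Section 9.3.4).** It rates redness, swelling and dryness. Its open question might bring out blistering but would not grade it.
- **Erosion/ulceration row (Section 9.2.2).** It may pick up blisters that have ruptured, but not intact vesicles.
- **Photographs and pain VAS.** Both are collected, but neither has a rule for scoring vesicle extent.

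None of these grades how much of the lip is blistered.

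Two lesser gaps sit in the same row. Exactly 50% and exactly 75% pustules have no grade, and the denominator of the percentage is not stated.

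**The case against.** The row can be defended as a deliberate ranking by type of sign first (vesicles below pustules) and by pustule extent second. The erosion/ulceration row does something similar: its Grade 4 is eschar or ulceration without any extent, placed above erosion of more than half. Whether extensive vesicles are worse than a few pustules is a clinical judgement that the documents do not settle. This stands, and it is a good reason not to dismantle the row.

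Visit timing also limits what better wording could recover. Under Section 4 the physician grades at Visits 2 to 6, that is, on treatment days and then six or more weeks later. Section 7.5 says local reactions usually settle within one to two weeks. Blistering that appears and resolves between visits goes ungraded however the row is written. This also stands.

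A reader might infer more than the documents support:

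- *That severe blistering gets the lowest grade.* The lowest grade is 0, for absence. Grade 1 is the lowest grade for a reaction that is present, and it openly means vesicles alone, so their presence is not hidden.
- *That the study is biased towards calling treatment well tolerated, because no Grade 3 or 4 vesiculation could appear without pustules.* No maximum-grade or Grade 3–4 summary is planned. The synopsis promises tabulation, Section 12.1 gives only a general statement about analysis, and no threshold or stopping rule uses the item. The bias would depend on a summary that nobody has specified.
- *That the row misses the main reaction the protocol expects.* Blistering is listed among the less frequent possibilities, and no frequency is given.

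None of this supplies a grade for vesicle extent, so the narrower point remains.

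**Conclusion.** The point holds as a limited measurement gap. For vesicle-only reactions the row has one positive value, so isolated and extensive blistering cannot be told apart, and no other planned assessment clearly makes the distinction. This follows from the definitions alone and requires no assumption about rates.

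Its practical size cannot be estimated. The documents do not say how many of the 20 subjects might blister, how many would do so without pustules, or how much of it would be visible on a treatment day. It also rests on reading blistering as part of the expected PDT profile, which the Section 10 list suggests but does not define. The consequence is confined to the descriptive tolerability tabulation, and the clearance assessment is unaffected. The gap is worth closing because the remedy is cheap, not because a conclusion of the study depends on it.

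**What to change.** Keep the existing row, so that pustule extent and the ranking by type of sign are preserved. Add one CRF field, completed at the same assessments, for vesicle extent as a percentage of the treated lip. Use bands that neither overlap nor leave gaps, for example none, above 0 to below 50%, 50–75%, and above 75%. Stating the treated lip as the denominator removes the ambiguity for the new field.

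Tabulate vesicle extent beside the existing grade at each visit, and say in the tolerability summary that Grade 1 on the existing row is not to be read as mild blistering.

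Regrading the whole row by combined extent, with pustules reduced to yes/no, would be a poorer choice, because it gives up pustule extent to gain vesicle extent.

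The cost is one additional field to complete and tabulate. No extra visit, procedure or staff is needed. The field will not capture blistering that comes and goes between visits.
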